## 6 GENERAL ANALYSIS DEFINITION

Data collected throughout the study will be summarized using descriptive statistics and listed in the by-subject listings. The continuous variables will be summarized by descriptive statistics (n, mean, SD, median, minimum, and maximum). Categorical variables will be summarized with frequency and percentage. Summaries will be provided by treatment group within appropriate analysis populations, and by time point/time period, as appropriate. Baseline is defined as the last observation before the first dose of study drug administration except for the parameters specified below.

Primary evaluation period is defined as Weeks 10 to 12 and the secondary evaluation period is defined as Weeks 18 to 20.

Study day is defined as follows:

Study Day= [Event date – First dosing date + 1] if after first dosing date  
[Event date – First dosing date] if before first dosing date.

Note that with the definition above, days of "0" will not be used. As such, the study day can be interpreted as the number of days before or after first day of dosing. Event date refers to the date associated with the result being summarized. In some cases, this is the date of an assessment or measurement; in other cases, this is the onset date of an adverse or outcome event.

Assessments will be assigned to analysis visits based on the date the assessment took place regardless of the CRF page completed (i.e., scheduled visit number). Assessments will be mapped to visits based on Study Day.

If more than 1 Hb result is available in an analysis time period post-baseline, the average of all observed values will be assigned to that period. When more than 1 assessment is made for other measures within a given visit window post-baseline, the value of the assessment closest to the scheduled visit should be used. If the assessments are equally close, the value from the last assessment should be used.

If the central laboratory uses assays that have lower limits of detection (LLD), all laboratory results below the LLD will be imputed with the LLD. Results reported as greater than a value (i.e., “> value”) will be imputed as  $1.5 \times$  that value.

For subjects whose reference date is missing, the study day will also be categorized as missing.

*Adverse event onset*

- If onset date is completely missing, date is set to date of first dose.
- If year is present and month and day are missing or year and day are present and month is missing:

---

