- If year = year of first dose, then set month and day to month and day of first dose.
- If year < year of first dose, then set month and day to December 31.
- If year > year of first dose, then set month and day to January 1.
- If month and year are present and day is missing:
  - If year = year of first dose and
    - month = month of first dose, then set day to day of first dose date.
    - month < month of first dose, then set day to last day of month.
    - month > month of first dose, then set day to first day of month.
  - If year < year of first dose, then set day to last day of month.
  - If year > year of first dose, then set day to first day of month.
- For all other cases, set date to date of first dose.

*Adverse event end date*

- If year is present and month and day are missing or year and day are present and month is missing, set end month and day to December 31.
- If month and year are present and day is missing, set the day to last day of the month.
- If fatal event, date is set to minimum of imputed end date and death date.
- For all other cases, set date to missing.

The following [table](#) provides the convention to classify assessment dates into protocol-defined visits. The time windows reflect the administrative range around each visit. These windows are wider than those stated in the protocol.

Table 1. Classification of assessments at every visit during the study

| Target week / day                  | Actual visit day              | Visit / Week classification    |
|------------------------------------|-------------------------------|--------------------------------|
| Week 0 / Day 1                     | Day 1                         | Visit 1 / Week 0               |
| Week 1 / Day 8                     | Day 2-11                      | Visit 2 / Week 1               |
| Week 2 / Day 15                    | Day 12-21                     | Visit 3 / Week 2               |
| Week 4 / Day 29                    | Day 22-35                     | Visit 4 / Week 4               |
| Week 6 / Day 43                    | Day 36-49                     | Visit 5 / Week 6               |
| Week 8 / Day 57                    | Day 50-63                     | Visit 6 / Week 8               |
| Week 10 / Day 71                   | Day 64-74                     | Visit 7 / Week 10              |
| Week 11 / Day 78                   | Day 75-81                     | Visit 8 / Week 11              |

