## 7 SAMPLE SIZE JUSTIFICATION

Sample size is not based on a power analysis. Sample size reflects the exploratory nature of this study.

Approximately 95 subjects are planned for enrollment in the Main study with 40 and 55 subjects randomized to the low epoetin alfa dose group and the high epoetin alfa dose group, respectively. Approximately 30 subjects are planned for enrollment in the ESA hyporesponder parallel study.

Enrollment may be increased by up to approximately 20 additional subjects in the Main study and by up to approximately 30 additional subjects in the ESA hyporesponder parallel study to ensure adequate data are captured for the primary, PK/PD, and safety endpoints.

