## 8 STUDY ANALYSES

### 8.1 General Consideration

The following rules will be adopted when summarizing the data:

1. The Main Study and the ESA Hyporesponder Parallel Study will be summarized separately, but in an analogous manner, for all endpoints.
  - a. For the Main study, the low epoetin dose group ( $\leq 90$  U/kg/week), 450 mg of vadadustat, 300 mg of vadadustat and epoetin will be displayed side by side. In addition, the total vadadustat will be presented as well.
  - b. For the Main study, the high epoetin dose group ( $> 90$  and  $< 300$  U/kg/week), 600 mg, 450 mg, 300 mg of vadadustat and epoetin will be displayed side by side. In addition, the total vadadustat will be presented as well.
  - c. For the Main study, a summary of total vadadustat vs. epoetin will be presented as well. For the background information, a total column for all randomized patients will be presented except certain PK/PD parameters.
  - d. For the ESA Hyporesponder Parallel Study ( $\geq 300$  U/kg/week), 600 mg and epoetin will be displayed side by side.
2. For efficacy data analysis, 3 tables will be presented for some selected efficacy endpoints:
  - a. Overall summary by week including the first weeks and post Week 12 by treatment group which is based on the randomized dose group.
  - b. For subjects who switched Vadadustat dosing from QD to TIW dosing.
  - c. For subjects who did not switch from QD to TIW dosing after Week 12.
3. For safety data analysis, 5 sets of tables will be presented for some selected safety parameters:
  - a. Overall summary for all weeks including the first 12 weeks and post Week 12 by treatment group
  - b. Overall summary for the first 12 weeks of treatment.
  - c. Overall summary for Weeks 12 to the end of study for both switched and not switched patients at Week 12
  - d. Overall summary for Weeks 12 to the end of study for switched patients
  - e. Overall summary for Weeks 12 to the end of study for not switched patients
4. For patients who switched Vadadustat dosing from QD to TIW dosing at week 12, and then switched back to QD, if there are less than or equal to 20 subjects, only patient

---

listings/profiles will be created. If there are more than 20 patients, summary tables will be created by treatment groups for efficacy and safety.

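### Partial adverse event onset dates are imputed from first dose alone, so events after the Week 12 switch can be moved only into the first 12 weeks, never the other way

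*SAP*

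**What the plan says.** Section 6 (adverse event onset) handles on-treatment partial dates as follows:

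- No date at all: "If onset date is completely missing, date is set to date of first dose".
- Month missing, or month and day missing: "If year = year of first dose, then set month and day to month and day of first dose"; "If year > year of first dose, then set month and day to January 1".
- Day missing, year of first dose: "month = month of first dose, then set day to day of first dose date"; "month > month of first dose, then set day to first day of month". In a later year the day is likewise set to the first of the month.

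Onsets known to precede first dose go the other way. With the month missing, "If year < year of first dose, then set month and day to December 31"; with only the day missing, the last day of the month is used.

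No onset rule refers to the Week 12 switch, the first TIW dose or the end date of the event. Section 6 also takes the onset date as the event date when study day is derived for adverse events.

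Section 8.1, item 3, plans safety tables for all weeks (3a), for the first 12 weeks (3b) and for Weeks 12 to the end of study (3c to 3e), including "Overall summary for Weeks 12 to the end of study for switched patients". Section 10.1 tabulates treatment-emergent events by treatment period. Section 2.1.2 makes the safety of TIW dosing a secondary objective.

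**The concern.** The onset rules are built to answer one question: did the event begin after first dose? For that purpose, placing an uncertain on-treatment event as early as first dose allows is cautious, because it keeps the event treatment-emergent.

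The period tables ask a second question: did the event begin before or after the Week 12 switch? For that, the same rule errs in one direction. An event in the month of the switch with the day missing lands on the first of that month, normally before the switch. One with the month missing in the first-dose year lands on Day 1. No partial date from the daily period can be carried past the switch.

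What is at stake is the count of events in Weeks 12 onward, above all in the switched-subject table that serves the TIW safety objective. About 95 subjects are planned in the Main study and 30 in the ESA hyporesponder parallel study, and switchers are only some of the vadadustat subjects. In tables that small, one serious or special-interest event in the wrong period can change how they read.

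**Working it through.** The SAP has no figure to reproduce here: Section 7 states that "Sample size is not based on a power analysis", and Section 10.1 makes safety analysis descriptive. The check is therefore an enumeration of the Section 6 rules.

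**Inputs from the SAP.** The onset rules above; Week 12 at target Day 85 and Week 20 at target Day 141 (Section 6, Table 1); follow-up to Week 24 (Section 3.5), taken as 24 × 7 = Day 168.

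**Assumptions.** First-dose dates uniform over the 365 days of 2019 (the SAP gives no enrolment calendar); onsets uniform over days; last daily-dosing day = Day 85; period decided by the imputed onset date.

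**Formula.** Share moved = (start date, onset day) pairs with true onset after Day 85 but imputed study day ≤ 85, divided by all pairs with true onset after Day 85. The denominators are 365 × 56 = 20,440 (Days 86 to 141) and 365 × 83 = 30,295 (Days 86 to 168).

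| Missing part | To Day 141 | To Day 168 |
|---|---|---|
| Day | 5,395 / 20,440 = 26.4% | 5,395 / 30,295 = 17.8% |
| Month | 18,844 / 20,440 = 92.2% | 26,809 / 30,295 = 88.5% |
| Whole date | 100% | 100% |

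The day-missing numerator is the same in both columns because only onsets in the calendar month of the switch can move.

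**Spread by start date.** Day missing: 0% to 53.6% (to Day 141) or 0% to 36.1% (to Day 168). Month missing: 0% to 100%. With the boundary at Day 84 or Day 88 instead, the day-missing share to Day 141 is 25.9% or 27.9%.

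**Reverse error.** Over 365 × 85 = 31,025 pairs with true onset on Days 1 to 85, none is imputed after Day 85, whichever part is missing.

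**Example.** First dose 1 August 2019, so Day 85 is 24 October. A true onset on 25 October with day missing becomes 1 October (Day 62) and moves to the daily period. A true onset on 18 November becomes 1 November (Day 93) and stays in Weeks 12 onward.

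**Effect on the tables.** If a share f of Weeks 12 onward events lacks only the day, the fraction lost is between 0.178 × f and 0.264 × f. Assumed values of f give:

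- f = 2%: about 0.4% to 0.5%
- f = 5%: about 0.9% to 1.3%
- f = 10%: about 1.8% to 2.6%

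**Cost of the opposite rule.** Suppose every event that could have begun after Day 85 were sent to Weeks 12 onward. Of true daily-period onsets, 5,376 / 31,025 = 17.3% with day missing, 27,370 / 31,025 = 88.2% with month missing and 100% with no date would move, before any screen on end date.

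**The case against.** The strongest reply is that the rule suits its evident purpose, treatment emergence, and that its side effect is small and unquantified. Several parts of this stand.

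- A reader might infer that the rules always choose the earliest possible day. They do not. Onsets known to precede first dose go to the last day of the month or to December 31, and onsets in the first-dose month go to the first-dose day, not the 1st. The point is confined to on-treatment events.
- A reader might infer that the day-missing rule empties the TIW period. It misplaces only events in the calendar month of the switch. The large shares come from missing months and missing dates.
- The 26% figure stops at Week 20, whereas items 3c to 3e run to the end of study. With that longer window the share is about 18%.
- A reader might infer that TIW dosing will look safer than epoetin alfa. The documents do not support this. The same rules apply to epoetin alfa and to vadadustat subjects who stay on daily dosing, so groups compared within Weeks 12 onward are affected alike. The daily-versus-TIW contrast within vadadustat is already non-randomised, because switchers must meet the transition criteria.
- The SAP never states how events are allocated to periods. That the imputed onset date is used is an inference from Section 6, though a reasonable one, since no other onset date is supplied.
- Section 10.1 counts subjects once per preferred term, so a moved event changes a row only if the subject has no other event of that term in the period.

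These limits bear on size and reach. None reverses the direction or supplies the missing allocation rule.

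**Conclusion.** The point holds as a minor but real defect. A stated rule, applied to a purpose it was not built for, misplaces partially dated post-switch events in one direction only. Of the affected events, about 18% to 26% with day missing, 88% to 92% with month missing and all with no date would be credited to the first 12 weeks; the reverse error is zero. These shares rest on uniform start dates over one year, a switch at Day 85, uniform onsets, and use of the imputed date for period allocation.

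What is distorted is the absolute count in Weeks 12 onward and the within-vadadustat contrast of daily with TIW dosing. The all-weeks table is not changed by movement between periods. That TIW dosing will in fact appear safer is a possible direction, not a demonstrated result, because the SAP does not give the share of partial dates.

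**What to change.** Keep the present onset rules for treatment-emergent status only, and add a period-allocation rule to Section 6 for the tables in Section 8.1, items 3b to 3e, and Section 10:

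1. Where the known date parts and the reported end date determine the period, place the event there. The reported end date should be used because the Section 6 end-date rules push partial end dates to month-end or December 31, where they rarely exclude anything.
2. Where the partial date fits both sides of the subject's switch date (the Week 12 date for subjects who did not switch), assign the event to Weeks 12 onward in those tables, as the conservative allocation for TIW.
3. Present alongside, by treatment group, the number of such events and the results under the alternative allocation to the first 12 weeks.

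The cost is a short addition to Section 6, one derived variable and an additional display. The downside is that step 2 alone reverses the bias: before the end-date screen it would move about 17% of true daily-period onsets with day missing, about 88% with month missing and all undated ones. Both allocations must therefore be shown. The change concerns data handling only and leaves dosing and treatment-emergent status as they are.

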### 5.3 Other Secondary Efficacy Endpoints

- Mean change in Hb between Baseline (average pretreatment Hb) and the secondary evaluation period (average Hb from Weeks 18 to 20)
- Proportion of subjects with Hb values within the target range (10.0 to 11.0 g/dL, inclusive) at the secondary evaluation period (Weeks 18 to 20)
- For subjects who transitioned to TIW vadadustat dosing, proportion of subjects with Hb values within the target range (10.0 to 11.0 g/dL, inclusive) at the secondary evaluation period (Weeks 18 to 20)
- Proportion of subjects with a mean increase in Hb from Baseline to the primary evaluation period  $\geq 0.5$  g/dL (average Hb from Weeks 10 to 12) or with Hb values within the target range (10.0 to 11.0 g/dL, inclusive) at the primary evaluation period (Weeks 10 to 12)
- Proportion of subjects with a mean increase in Hb from Baseline to the secondary evaluation period  $\geq 0.5$  g/dL (average Hb from Weeks 18 to 20) or with Hb values within the target range (10.0 to 11.0 g/dL, inclusive) at the secondary evaluation period (Weeks 18 to 20)
- Intravenous (IV) iron supplementation
- ESA rescue
- RBC transfusion

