| Week 12 / Day 85                   | Day 82-88                     | Visit 9 / Week 12              |
| Week 13 / Day 92                   | Day 89-95                     | Visit 10 / Week 13             |
| Week 14 / Day 99                   | Day 96-105                    | Visit 11 / Week 14             |
| Week 16 / Day 113                  | Day 106-119                   | Visit 12 / Week 16             |
| Week 18 / Day 127                  | Day 120-133                   | Visit 13 / Week 18             |
| Week 20 / Day 141                  | Day 134 - (last dose day + 7) | Visit 14 / Week 20             |
| Follow up / Day last dose day + 28 | ≥ last dose day + 8           | Visit 15 / Week 24 (Follow up) |

Note: Week 20 is the end of treatment.

It is expected that some subjects will discontinue Follow-Up. The reasons for any missing data will be summarized by treatment arm. The primary analysis will be based upon observed data without imputation. As a sensitivity analysis for primary efficacy endpoint, missing Hb in weeks 10 to 12 will be imputed using last observation carried forward (LOCF). Similarly, for certain secondary efficacy endpoints, missing Hb in weeks 18-20 will be imputed using LOCF.

---

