## 8.9 Study Medication Exposure and Compliance

Study medication exposure and compliance will be summarized using descriptive statistics for the FAS and Safety Population. Study medication and subject dosing diary data will also be presented in data listings.

The calculated compliance rate for a given time period will be derived from exposure data as the number of days on dosing period collected on electronic case report forms (eCRFs) divided by the number of days in that time period.

Compliance will be summarized as follows:

- Descriptive statistics will be summarized by treatment group for entire treatment period.
- Percent compliance will be categorized according to the following categories for entire treatment period for safety population by treatment group:
  - less than 50% (significant drug noncompliance)
  - at least 50%, less than 80% (moderate drug noncompliance)
  - greater or equal 80% (drug compliance)
  - unknown

Study medication exposure and compliance will be summarized for the first 12 weeks, Weeks 12 – 20, and entire treatment period for each treatment group. In addition, for Weeks 12 – 20, patients who switched from daily vadadustat dose to TIW and patients who did not switch at Week 12 will be summarized separately.

For epoetin alfa group, increases in dose relative to last dose will be characterized in the following categories by percentage increase: <50%,  $\geq 50\%$  and <100%, and  $\geq 100\%$ . Subjects will be presented by their maximum category of increase for the first 12 weeks, Weeks 12 – 20, and entire treatment period.

Dose change information including the following categories will be summarized for the first 12 weeks and Weeks 12 – 20 treatment period for each treatment group:

- Dose not changed
- Protocol guided dose reduction
- Dose increased based on Hb assessment
- Dose decreased based on Hb assessment

---

- Dose interrupted based on Hb assessment
- Dose decreased due to adverse event
- Dose interrupted due to adverse event
- Dose restarted
- Transitioned from QD to TIW dosing
- Converted back from TIW to QD dosing

---

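### Table 1 ends Week 20 at last dose day + 7, so an on-time Week 20 Hb taken during a dose hold can be classified as follow-up and lost from the Weeks 18-20 endpoints

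*SAP*

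**What the plan says.** SAP section 6, Table 1, gives every visit from Week 1 to Week 18 a window with fixed day limits. The Week 20 row, with target "Week 20 / Day 141", is different: its window is "Day 134 - (last dose day + 7" days. The follow-up row takes any assessment at "≥ last dose day + 8" and has no minimum study day.

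Section 6 also fixes how values reach these rows: "Assessments will be assigned to analysis visits based on the date the assessment took place regardless of the CRF page completed". When a period contains several Hb results, their average is used. It further states that "the secondary evaluation period is defined as Weeks 18 to 20".

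Section 8.9 lists "Dose interrupted based on Hb assessment" among the dose-change categories, separately from restarts, and counts it for Weeks 12-20 as well as for the first 12 weeks.

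Five endpoints rest on the Weeks 18-20 period:

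- Section 5.2 (key secondary): the change from Weeks 10-12 to Weeks 18-20 in subjects who moved to TIW dosing.
- Section 5.3: "Mean change in Hb between Baseline (average pretreatment Hb) and the secondary evaluation period (average Hb from Weeks 18 to 20"; the in-range proportion overall; the in-range proportion in TIW subjects; and the composite of a rise of at least 0.5 g/dL or an in-range Hb.

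**The concern.** The boundary between Week 20 and follow-up depends on the last dose taken. It does not depend on whether the subject has stopped study drug for good or has had the end-of-treatment visit. A note to Table 1 makes Week 20 the end of treatment, so a hold still in force at Week 20 has no later dose to move the boundary. The subject can be on study and on time, and still have the Week 20 Hb counted as follow-up.

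The loss would not be random. The holds in question are made because of Hb, and Hb is the endpoint. Treatment-period values would also enter the follow-up summary, and the by-week Week 20 summary would lose them.

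**Working it through.** **Inputs, all from Table 1 in section 6.** Let L be the last dose day.

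- Week 18: target Day 127, window Day 120-133.
- Week 20: target Day 141, window Day 134 to L + 7.
- Follow-up: any day from L + 8.
- There is no Week 19 row, so no visit is scheduled between Day 127 and Day 141.

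**Normal operation.** With L = 141, Week 20 runs from Day 134 to 141 + 7 = Day 148. With L = 140 it runs to Day 147. The table works when dosing continues to Week 20.

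**When an on-time Week 20 Hb is lost.** Day 141 is follow-up when 141 ≥ L + 8, that is, when L ≤ 133.

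**When the Week 20 window is empty.** This needs L + 7 < 134, that is, L ≤ 126.

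**When follow-up overlaps the Week 18 window.** This needs L + 8 ≤ 133, that is, L ≤ 125. An on-target Day 127 Hb meets both rows when L + 8 ≤ 127, that is, L ≤ 119.

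| L | Week 20 window | Class of Day 141 Hb | Follow-up starts |
|---|---|---|---|
| 141 | Day 134-148 | Week 20 | Day 149 |
| 134 | Day 134-141 | Week 20 | Day 142 |
| 133 | Day 134-140 | Follow-up | Day 141 |
| 130 | Day 134-137 | Follow-up | Day 138 |
| 127 | Day 134 only | Follow-up | Day 135 |
| 126 | empty | Follow-up | Day 134 |
| 125 | empty | Follow-up | Day 133 (inside Week 18) |
| 119 | empty | Follow-up | Day 127 (Week 18 target) |

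**Is the case realistic?** A hold prompted by an on-target Week 18 Hb and still in force at Week 20 is about 141 - 127 = 14 days old, twice the 7-day allowance. A hold that leaves L at Day 134 or later does no harm.

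**Effect on one subject (assumed Hb values).**

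- Week 18 Hb 12.3, Week 20 Hb 11.0: the average is (12.3 + 11.0)/2 = 11.65. With Week 20 moved out it is 12.3, a shift of +0.65. Both values are above 11.0, so target-range status does not change.
- Week 18 Hb 10.9, Week 20 Hb 11.5: the average is (10.9 + 11.5)/2 = 11.2, out of range. With Week 20 moved out it is 10.9, in range, a shift of -0.3.

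The two examples move in opposite directions.

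**Effect on an arm (also assumed).** Section 7 plans 40 and 55 subjects in the two strata. Equal allocation over 3 and 4 arms, which the SAP does not state, gives 40/3 = 13.3 and 55/4 = 13.8, or about 14 per arm. One to three subjects like the first example would move an arm mean by 1/14 × 0.65 = 0.05 to 3/14 × 0.65 = 0.14 g/dL. One change of target-range status would be worth 1/14, about 7 percentage points. These figures give a sense of scale and are not estimates.

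**The case against.** The best defence is that last dose + 7 days is the plan's own on-treatment limit. Section 9.3 uses it for iron use, ESA rescue and RBC transfusion as rescue. Whether an Hb taken more than a week off drug belongs in the endpoint is partly a choice of estimand. That much stands, but it does not justify this row. The SAP states no on-treatment rule for Hb, and the earlier windows apply none: an Hb drawn during a hold at Weeks 10-12 stays in its week once dosing resumes. Section 6 calls the windows administrative and wider than the protocol's, which does not fit a window that can shrink to nothing.

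Other limits also stand. The subject normally stays in the analysis through the Week 18 value, the by-subject listings still show the Week 20 Hb, and the analysis is exploratory and descriptive. The planned LOCF sensitivity analysis is not a remedy. The period is not missing when a Week 18 Hb exists, and when it is missing, an earlier value is carried forward although a later one was measured.

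A reader might infer more than the SAP supports:

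- **A bias of known size or direction.** The SAP gives no hold rule, frequency or duration. The illustrations point both ways, and nothing shows that the Hb pattern in the second one would lead to a hold.
- **An effect on the primary endpoint.** Its windows, Day 64-88, have fixed limits, so a hold at Week 20 takes nothing from them. The follow-up row could overlap them for someone who stopped drug long before, but that is a labelling ambiguity for early discontinuers and not this loss.

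**Conclusion.** The point holds as a defect in the visit-window rule. Applied as written, Table 1 removes an on-time Day 141 Hb from Week 20 whenever the last dose was on or before Day 133, and nothing in the SAP exempts the Hb-based interruptions it foresees. What is lost is usually one of the two scheduled Hb values in the period. The whole period value is lost only where there is no Week 18 Hb. One key secondary and four other secondary endpoints are exposed.

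The day limits follow from Table 1 without assumptions. The number of subjects affected cannot be derived from the SAP, and any g/dL or percentage-point figure depends on assumed Hb values, counts and arm sizes. The change should be made because the rule drops valid data for a reason tied to the outcome and is cheap to correct. No material distortion has been shown.

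**What to change.** Rewrite the last two rows of Table 1.

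1. For every subject not recorded in the disposition data (section 8.3) as having discontinued study drug early, let Week 20 run from Day 134 to the later of Day 148 and last dose day + 7. Start follow-up on the next day. Day 148 is the limit the table already gives when L = 141, and the two rows then cannot overlap. Section 3.5 places the safety assessment four weeks after Week 20, about Day 141 + 28 = Day 169, so a start at Day 149 still captures it.
2. For recorded early discontinuers, word the follow-up row so that it cannot overlap the fixed windows, and let an Hb taken in a scheduled window keep that week's label.
3. Flag each Hb taken more than 7 days after the last dose, so that an on-treatment summary can be shown as a sensitivity analysis.

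The cost is a small change to the visit-mapping program. Some off-drug Hb values will enter the Weeks 18-20 averages, and the flag makes their influence visible.
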